### *Drug Interactions*

**Avoid Concomitant Use** of Daunorubicin with any of the following: BCG; Natalizumab; Pimecrolimus; Tacrolimus (Topical); Vaccines (Live).

**Increased Effect:** Daunorubicin may increase the levels/effects of: Leflunomide; Natalizumab; Vaccines (Live).

The levels/effects of Daunorubicin may be increased by: Bevacizumab; Denosumab; P-Glycoprotein inhibitors; Pimecrolimus; Tacrolimus (Topical); Taxane Derivatives; Trastuzumab

**Decreased Effect:** Daunorubicin may decrease the levels/effects of: BCG; Cardiac Glycosides; Sipuleucel-T; Vaccines (Inactivated); Vaccines (Live)

The levels/effects of Daunorubicin may be decreased by: Cardiac Glycosides; Echinacea; P-Glycoprotein Inducers

**Ethanol/Herb/Nutraceutical Interactions:** Avoid ethanol (Due to GI irritation).

### *Pharmacokinetics*

**Distribution:**  $V_d$ : 40 L/kg; to many body tissues, particularly liver, spleen, kidney, lung, heart; does not distribute into the CNS; crosses placenta

**Protein binding, plasma:** 70% to 76%

**Metabolism:** Primarily hepatic to Daunorubicinol (active), then to inactive aglycones, conjugated sulfates, and glucuronides

#### **Half-life elimination:**

Distribution: 2 minutes

Elimination: 14-20 hours

Terminal: 18.5 hours

Daunorubicinol plasma half-life: 24-48 hours

**Excretion:** Feces (~40%); urine (~25% as unchanged drug and metabolites)

### *Nursing Guidelines*

- Drug is a potent vesicant. Establish patency of IV before and frequently during administration as to avoid extravasation. If drug is being administered IV push administer through side port of rapidly running IV solution. If suitable vein cannot be used, central venous access may become necessary. Discuss with treating MD. If extravasation occurs treat per your institution's policy.
- Drug is not compatible with heparin. Be sure to flush heparin locked IV's or central lines before administering agent.
- Moderate to severe nausea occurs in up to 50% of patient within first 24 hours. Administer antiemetics as ordered and assess for their effectiveness.
- Inform patient about alopecia
- Potent myelosuppressive agent. Monitor CBC closely. Inform patient to report any signs or symptoms of infection, or unusual bruising or bleeding.
- Drug is cardiotoxic. Maximum lifetime dose limit is 550 mg/m^2. Monitor for signs of acute cardiac toxicity, which is possible within hours after administration. This is unrelated to cumulative dose and may manifest symptoms of pump or conduction dysfunction. Watch for signs or symptoms of CHF, pericardial effusion, and transient ECG abnormalities.
- Monitor liver function tests. Dose reduction is necessary in patients with impaired liver function.
- Radiation recall is a possibility with this drug. Monitor patient's skin at site of previous irradiation for damage.
- Inform patient that urine may be pink or red for up to 48 hours after administration.

### *Adverse Events*

The most common adverse reactions associated with daunorubicin include hematologic, gastrointestinal, and cardiovascular. Leukopenia and thrombocytopenia are often dose-limiting. Daunorubicin causes nausea and vomiting, but is generally considered moderately emetogenic. Stomatitis is also common. Acute cardiovascular reactions include EKG abnormalities which are usually asymptomatic and self-limiting. Chronic cardiomyopathy manifests as congestive heart failure. Risk factors include age (> 70 years), mediastinal irradiation and cumulative lifetime dose (e.g., > 450 mg/m^2). Dermatologic reactions (alopecia, “radiation recall”) are also common. Less common are red/orange urine (more alarming than of notable consequence to patients) and skin “flare.” The flare consists of redness and itching along the distribution of the vessel through which daunorubicin was administered. It is usually self-limiting and of short duration, but should be distinguished from an extravasation reaction. Extravasation of daunorubicin does not occur very often, but can result in severe skin and tissue necrosis. Cold should be applied to the site of a suspected or actual extravasation of daunorubicin.

Please refer to the package insert for the comprehensive list of adverse events.

#### **10.4 Cytarabine Intravenous (Cytosar, Ara-C) (NSC #63878)**

##### *Procurement*

Commercial supplies. Pharmacies or clinics shall obtain supplies from normal commercial supply chain or wholesaler.

##### *Formulation*

Commercially available for injection, powder for reconstitution: 100 mg, 500 mg, 1 gram, 2 gram. Commercially available solution for injection in concentrations of 20 mg/mL and 100 mg/mL. Commercially available preparations may be preservative-free or preservative-containing.

##### *Preparation, Storage and Stability*

Store intact vials of powder at room temperature 15°C to 30°C (59°F to 86°F). Reconstitute with bacteriostatic water for injection. Reconstituted solutions are stable for up to 8 days at room temperature, although the manufacturer recommends use within 48 hours. Further dilution in 250-1000 mL of D5W or 0.9% NaCL is stable for 8 days at room temperature (25°C). Note: Solutions containing bacteriostatic agents should not be used for the preparation of either high doses or intrathecal doses of cytarabine.

##### *Administration*

Refer to the drug treatment section of the protocol for specific administration directions and infusion rates. May be given IV or subcutaneously.

##### *Drug Interactions*

Cytochrome P450 Effect: None known

Increased Effect/Toxicity: Cytarabine may increase the levels/effects of: Clozapine, Leflunomide, Natalizumab, Vaccines (Live). The levels of Cytarabine may be increased by: Denosumab, Pimecrolimus, Roflumilast, Tacrolimus (Topical); Trastuzumab

Decreased Effect: Cytarabine may decrease the levels/effects of: BCG, Cardiac Glycosides, Coccidioidin Skin Test, Flucytosine, Sipuleucel-T, Vaccines (inactivated); Vaccines (live).

Herb/Nutraceutical Interactions: Avoid Echinacea.

##### *Pharmacokinetics*

Distribution: Vd: Total body water; widely and rapidly since it enters the cells readily; high-dose cytarabine crosses the blood-brain barrier with CSF levels of 40% to 50% of plasma level

Metabolism: Primarily hepatic; metabolized by deoxycytidine kinase and other nucleotide kinases to aracytidine triphosphate (active); about 86% to 96% of dose is metabolized to inactive uracil arabinoside.

Half-life elimination: I.V.: Initial: 7-20 minutes; Terminal: 1-3 hours.

Excretion: Urine (~80%) within 24 hours

#### *Nursing Guidelines*

- Can be a potent myelosuppressive agent. Monitor CBC closely. Anemia, leukopenia, and thrombocytopenia are expected. Nadir within 5-7 days with recovery expected in 2-3 weeks. Hematological toxicity is more intense if ARA-C is given as a continuous IV infusion versus an IV bolus.
- Nausea and vomiting is dose-related, common, and often preventable with antiemetic drugs. Administer as ordered and assess for their effectiveness.
- Instruct patient of possibility of metallic taste. The use of sugarless hard candies may lessen this effect.
- Stomatitis is possible.
- May cause pancreatitis or peritonitis. Instruct patient to report any severe or worsening abdominal pain immediately.
- Monitor LFT's-elevations of LFT's may occur.
- Cerebellar toxicity can occur in 16-40% of patients with more severe symptoms at higher doses. Monitor for these toxicities with each dose of ARA-C. Signs and symptoms of cerebellar toxicity can include: lethargy with progressive confusion, ataxia, nystagmus, slurred speech. Report any of these or other neurological changes to the MD immediately.
- Instruct patient to report any shortness of breath or difficulty breathing as this may be a sign of a rare but life threatening pulmonary complication.
- Monitor for signs of conjunctivitis and/or keratitis. This is usually prevented with prophylactic glucocorticoid eye drops.
- Assess for skin rash. This may present itself as an erythema without exfoliation, or a generalized rash. Report to MD.
- Monitor for "ARA-C" syndrome. This is characterized by bone and muscle pain, chest pain, fever, general weakness, reddened eyes, and skin rash. Report these to the MD, as patient may need to be treated with corticosteroids.

#### *Adverse Events*

The most common adverse reactions reported with cytarabine ("usual dosage" e.g.,  $\leq 200$  mg/m^2/day) include hematologic, gastrointestinal, dermatologic, and hepatic. Myelosuppression includes neutropenia, thrombocytopenia and anemia. Cytarabine is considered highly emetogenic. In addition to nausea and vomiting, diarrhea and mucositis are reported in  $> 10\%$  of patients receiving cytarabine. Alopecia is common. Rash, including hand-foot syndrome, is reported also. Mild jaundice, and elevated transaminase levels also are reported in  $> 10\%$  of patients. Fever (non-infectious) is also reported among the most common adverse reactions associated with cytarabine. Less commonly, a "cytarabine syndrome" or "ara-C syndrome" has been reported. The syndrome may be characterized by fever, myalgia, bone pain, rash, malaise, and chest pain.

In addition to the above, the following adverse reactions have been described with high dose ( $\geq 1$  gm/m^2/day) cytarabine. Neurologic toxicity is primarily cerebellar (nystagmus, dysarthria, dysdiadochokinesia, ataxia, abnormal gait) but cerebral toxicity (somnolence, confusion, psychosis, seizures) may also be seen. Ocular toxicity including photophobia and conjunctivitis are described with high dose cytarabine. Steroid ophthalmic solution should be administered, beginning 6-12 hours before cytarabine and continuing for 24 hours after the

last “high dose”, to prevent conjunctivitis. Pulmonary edema has been rarely reported in association with high dose cytarabine.

Please refer to the package insert for the comprehensive list of adverse events.

## 11.0 MEASUREMENT OF EFFECT

Response to treatment will be assessed according to the Revised Recommendations of the International Working Group for Diagnosis, Standardization of Response Criteria, Treatment Outcomes, and Reporting Standards for Therapeutic Trials in Acute Myeloid Leukemia [24].

### 11.1 Morphologic complete remission (CR)

Defined as morphologic leukemia-free state, including < 5% blasts in BM aspirate, no blasts with Auer rods, no persistent extramedullary disease, ANC  $\geq$  1,000/ $\mu$ l and platelet count  $\geq$  100,000/ $\mu$ l. The patient must be free of the need for RBC transfusions.

### 11.2 Cytogenetic complete remission (CCyR)

Only patients with an identified cytogenetic abnormality pretreatment may receive this designation. Defined as a morphologic complete remission plus reversion to a normal karyotype (no clonal abnormalities detected in a minimum of 20 metaphase cells).

### 11.3 Morphologic complete remission with incomplete blood count recovery (CRi)

Defined as CR with the exception of neutropenia <1,000/ $\mu$ l or thrombocytopenia <100,000/ $\mu$ l.

### 11.4 Treatment failure (TF)

Treatment failure includes those patients for whom treatment has failed to achieve a CR or CRi and will be classified as follows:

- Treatment failure due to resistant disease includes patients who survive at least 7 days after completion of the final dose of the initial course of treatment but whose last posttreatment peripheral blood smear and/or bone marrow sample showed persistent AML.
- Treatment failure due to complications from aplasia includes patients who survive at least 7 days after the final dose of the initial course of treatment and die while cytopenic, but whose last posttreatment bone marrow was aplastic or hypoplastic, as determined by the institutional morphologist or pathologist, without evidence of leukemia, provided that marrow was obtained within 7 days of death.
- Treatment failure of indeterminate cause includes three categories of patients:
  - Patients who die less than 7 days after conclusion of the initial course of treatment, and
  - Patients who die 7 or more days after the conclusion of treatment whose most recent peripheral blood smear did not show persistent leukemia and who did not have a bone marrow examination subsequent to therapy
  - Patients who die without completing the first course of therapy.

### 11.5 Recurrence/morphologic relapse

Defined as reappearance of blasts in the blood or the finding of  $\geq$  5% blasts in the BM, not attributable to any other cause.

## 12.0 END OF TREATMENT/INTERVENTION

### 12.1 Duration of Protocol Treatment

Patients will continue with the therapy specified in this protocol until one of the following occurs:

- Completion of all protocol-specific treatments.
- Unacceptable toxicity.
- Treatment failure due to resistant disease or death.
- Recurrence / morphologic relapse.
- Withdrawal of consent by the patient to continue on study.

### 12.2 Criteria for Discontinuation of Protocol Treatment/Intervention

In the absence of treatment delays due to adverse event(s), treatment may continue until one of the following criteria applies:

- Completion of all protocol-specified therapy
- Recurrence/morphologic relapse
- Intercurrent illness that prevents further administration of treatment
- Unacceptable adverse event(s)
- Patient decides to withdraw from the study
- General or specific changes in the patient's condition render the patient unacceptable for further treatment in the judgment of the investigator
- Patient non-compliance
- Termination of the study by sponsor

The reason(s) for protocol therapy discontinuation, the reason(s) for study removal, and the corresponding dates must be documented in the Case Report Form (CRF).

### 12.3 Follow-up

#### 12.3.1 Duration of Follow-up

Patients who complete protocol therapy will go to clinical follow-up, followed every 2 months until 1 year after completion of therapy, every 3 months between 1 and 2 years after completion of therapy, then every 6 months for up to 5 years from study registration or until relapse.

#### 12.3.2 Follow-up for Patients who Stop Study Treatment/Intervention Early

Patients who end treatment for reasons other than relapse and subsequent treatment other than oral azacitidine per [Section 8.1.1](#) will go to clinical follow-up, followed every 2 months until 1 year from the date of discontinuation, then every 3 months until 2 years from the date of discontinuation, then every 6 months for up to 5 years from registration or until relapse.

Patients who relapse or receive a subsequent treatment other than transplantation or azacitidine per [Section 8.1.1](#) will go to survival follow-up, followed every 6 months from the date of discontinuation for 5 years from registration.

Patients who receive transplantation will be removed from this protocol and go to clinical follow-up, followed every 3 months for 2 years and then every 6 months up to 5 years from registration.

Patients who withdraw prior to starting any protocol treatment will go to survival follow-up, followed every 6 months for up to 5 years in observation from registration.

### **12.2.3 Follow-up for Specimen Submission**

Specimen submission must continue during all treatment stages, observation and clinical follow-up. Specimen submission are not required if patient is in survival follow-up.

## **12.4 Extraordinary Medical Circumstances**

If, at any time the constraints of this protocol are detrimental to the patient's health and/or the patient no longer wishes to continue protocol therapy, protocol therapy shall be discontinued. In this event:

- Document the reason(s) for discontinuation of therapy on data forms.
- Follow the patient for protocol endpoints as required by the Study Calendar.

## **12.5 Managing ineligible patients and registered patients who never receive protocol intervention**

### **Definition of ineligible patient**

A study participant who is registered to the trial but does not meet all of the eligibility criteria is deemed to be ineligible.

### **Follow-up for ineligible patients who continue with protocol treatment**

Patients who are deemed ineligible after registering may continue protocol treatment, provided the treating physician, study chair, and executive officer agree there are no safety concerns if the patient continues protocol treatment. All scans, tests, and data submission are to continue as if the patient were eligible. Notification of the local IRB may be necessary per local IRB policies.

### **Follow-up for ineligible patients who discontinue protocol treatment**

For patients who are deemed ineligible after registering to the trial, who start treatment, but then discontinue study treatment, the same data submission requirements are to be followed as for those patients who are eligible and who discontinue study treatment.

### **Follow-up for patients who are registered, but who never start study treatment**

For all study participants who are registered to the trial but who never receive study intervention (regardless of eligibility), the follow-up requirements are specified below.

Baseline, off treatment, and post-treatment follow up (i.e., relapse, progression, and survival) data submission required. See the Data Submission Schedule accompanying the All Forms Packet.

## **13.0 STATISTICAL CONSIDERATIONS**

### **13.1 Study Design**

This is an open-label, randomized phase II/III study.

The primary objective of the Phase II study is to determine based on the event-free survival (EFS) whether the combination of uproleselan plus daunorubicin/cytarabine should be tested further against standard of care: daunorubicin/cytarabine in the phase III component of this trial.

The primary objective of the Phase III study is to compare the OS between uproleselan plus daunorubicin/cytarabine versus the control arm (daunorubicin/cytarabine). Patients accrued during the Phase II portion of the trial will be used in the Phase III analysis.

Randomization: Randomization will be stratified on the following stratification factors: age (60-69 vs. 70 and older), performance status (0-1 vs. 2-4), de novo vs. secondary/therapy related AML. Patients will be randomized to receive one of the two treatment regimens with equal allocation using a permuted block method to balance the stratification factors.

### 13.1.1 Primary Endpoint

- Phase II component: Event-free survival (EFS). EFS is defined as the time from the date of randomization to the first of failure to achieve a CR/CRi during induction, relapse, or death due to any cause, with patients last known to be alive and event-free censored at the date of last contact. Patients who are removed from protocol treatment for allogeneic HCT or azacitidine per [Section 8.1.1](#) will not be censored for EFS, and will be continued to be followed for relapse or death. Patients who receive other non-protocol therapy without relapse or CR/CRi during induction will be censored at the time they discontinue the treatment. All randomized patients meeting the eligibility criteria will be evaluable for the primary endpoint (EFS) analysis based on an intention to treat.
- Phase III component: Overall survival (OS) – measured from the date of randomization to death from any cause, with patients last known to be alive censored at the date of last contact. All randomized patients will be evaluable for this endpoint.

*As of Amendment 04, there will be no additional accrual to the Phase III component of the trial regardless of the outcome of the Phase II analysis.*

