- 3 Monitoring of serum creatinine, bilirubin, AST/ALT/Alk Phos should be performed prior to the start of each cycle of treatment and then as clinically indicated.
- 4 Baseline bone marrow biopsy/aspirate should be obtained at the time of pre-registration and specimens should be submitted as outlined in [Section 6.2](#) (see also [Sections 3.2](#) and [4.4](#)).
  - A Day 14 of first course (+3 days)
  - B Cytogenetics are required prior to initiation of therapy, at achievement of first complete remission (if diagnostic specimen is abnormal), at the end of consolidation (if CR cytogenetics are abnormal), and at first relapse. After local review is complete, the designated local cytogeneticist will submit electronic karyotypes, metaphases, karyotype processing information, and FISH information (if applicable). See [Section 14.1](#).
  - C Bone marrow assessments post-treatment are only required if clinical or laboratory signs of relapse are present.

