### 13.2.2 Secondary Endpoints

- 1-year EFS rate:** The 1-year EFS rate is the proportion of efficacy evaluable patients event-free 1 year from registration. Patients who fail to achieve a CR/CRI during the induction, relapse, or die prior to 1 year after randomization/registration will be considered as a failure for this endpoint. Patients who are removed from protocol treatment for allogeneic HCT will continue to be followed for relapse or death at 1 year. Patients who are removed from study for other non-protocol therapy without relapse or CR/CRI during induction are also considered as a failure for the 1-year EFS endpoint.
- Disease-free survival (DFS):** DFS will be calculated as the time from achieving a CR/CRI to the time of relapse and/or death. Any patients who have not achieved the event of interest will be censored at the time of their last evaluation.
- Complete Remission (CR) and overall response rates:** Response to treatment will be assessed according to the Revised Recommendations of the International Working Group for Diagnosis, Standardization of Response Criteria, Treatment Outcomes, and Reporting Standards for Therapeutic Trials in Acute Myeloid Leukemia.
- Toxicity and tolerability:** As per NCI CTCAE v5.0, the term toxicity is defined as adverse events that are classified as either possibly, probably, or definitely related to the study treatment. The maximum grade for each type of toxicity will be recorded for each patient, and frequency tables will be reviewed to determine toxicity patterns. In addition, we will review all adverse event data that is graded as 3, 4, or 5 and classified as either “unrelated” or “unlikely to be related” to study treatment in the event of an

actual relationship developing. The incidence of severe (grade 3+) adverse events or toxicities will be described for each treatment arm, but will also be compared between the arms. Fisher's exact tests will be used to quantitatively compare the incidence of severe as well as specific toxicities of interest between the treatment arms and we will graphically assess differences in maximum grades observed for toxicities between the arms. Toxicity and tolerability will be monitored regularly. The study will be reviewable by the Alliance DSMB every 6 months to identify any toxicity or tolerability issues in either of the treatment arms.

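### EFS is censored at last contact but DFS, with the same post-remission events, at last evaluation; neither term is defined, so EFS can count some unassessed time as event-free

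*Combined protocol and SAP*

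**What the plan says.** Section 13.1.1 counts as an EFS event "the first of failure to achieve a CR/CRi during induction, relapse, or death due to any cause". Patients without an event are handled "with patients last known to be alive and event-free censored at the date of last contact". The OS bullet in the same section has the same anchor: "with patients last known to be alive censored at the date of last contact".

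Section 13.2.2 defines DFS as follows: "DFS will be calculated as the time from achieving a CR/CRI to the time of relapse and/or death". Its censoring rule differs: "Any patients who have not achieved the event of interest will be censored at the time of their last evaluation".

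Section 13.1.1 also has an exception for EFS: "Patients who receive other non-protocol therapy without relapse or CR/CRi during induction will be censored at the time they discontinue the treatment". Transplantation and oral azacitidine under Section 8.1.1 do not lead to censoring.

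No section defines last contact or last evaluation, or says why EFS and DFS differ. The sensitivity analyses in Section 13.2.4 deal with transplantation and with off-protocol treatment given because of MRD. None censors EFS at the last disease evaluation.

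**The concern.** From CR/CRi onward, EFS and DFS record the same two events, relapse and death. A patient still in remission can nevertheless have two different event-free dates under one plan.

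The date matters because relapse under Section 11.5 requires a finding in blood or marrow. Learning that a patient is alive settles OS status on that day, but not relapse status. If the last contact is later than the last assessment, the interval between them counts as event-free in EFS although nobody looked for relapse.

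EFS is the Phase II primary endpoint. Under Section 13.2.3 it is also the key secondary endpoint, tested at one-sided 0.025 if OS is significant, in a study labelled as an FDA registration study. The trial is open-label (Section 13.1), so the amount of contact-only follow-up could differ by arm.

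**Working it through.** **1. The plan's own figure.** Section 13.1.2 gives 96% power for HR 0.64 at one-sided 0.10 with 1:1 allocation, and Section 13.2.1 gives 191 events. By Schoenfeld's formula:

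power = Φ(√191/2 × |ln 0.64| − 1.2816) = Φ(6.910 × 0.4463 − 1.2816) = Φ(1.802) = 0.964.

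Freedman's formula at 96% power returns 191 events. With the accrual rates in Section 13.3 and exponential medians of 7 and 11 months, accrual ends at 29.8 months and 191.0 events are expected at 37 months. All of this agrees with the plan. The censoring date does not enter these formulas, so no stated number is in dispute.

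**2. The definitions side by side.**

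| Endpoint | Events | Censoring date |
|---|---|---|
| EFS (13.1.1) | no CR/CRi in induction, relapse, death | last contact |
| DFS (13.2.2) | relapse, death, counted from CR/CRi | last evaluation |
| OS (13.1.1) | death | last contact |

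**3. Where the two dates can differ.**

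- *In CR/CRi and in clinical follow-up, including after transplantation or oral azacitidine.* The calendar in Section 5.0 marks history and physical and CBC with differential at follow-up. On marrow it says: "Bone marrow assessments post-treatment are only required if clinical or laboratory signs of relapse are present". Blasts in the blood are enough for relapse under Section 11.5. A contact here is normally an assessment, so the gap is usually zero.
- *Already relapsed.* The EFS event has occurred, so censoring does not arise.
- *Other subsequent treatment while in CR/CRi.* Under Section 12.3.2 such a patient "will go to survival follow-up, followed every 6 months from the date of discontinuation for 5 years from registration". Whether EFS is censored at discontinuation depends on the exception quoted above. Read literally, it applies to patients with neither relapse nor CR/CRi in induction, so it does not clearly cover a patient in remission. If it does cover that patient, there is no gap. If it does not, the last-contact rule applies. Section 13.2.4 expects off-protocol treatment because of MRD, so the case is foreseen.
- *Withdrawal before any protocol treatment.* Section 12.3.2 sends these patients to 6-monthly survival follow-up, and Section 13.2.1 keeps all randomized patients in the analysis. Section 12.5 asks for relapse data on patients who never start treatment, which narrows this route.

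**4. Size, conditional on a gap.** Relapses unseen in credited time are roughly N × g × h, where N is the number of patients with a contact-only gap, g its mean length and h the monthly relapse hazard. The documents give none of the three. As an illustration, 262 − 191 = 71 patients have no event at the target. Assume that about 70 of them all have a 3-month gap, and that h is 0.01 to 0.03. Then 70 × 3 × 0.01 = 2.1 and 70 × 3 × 0.03 = 6.3 relapses, or 1.1% to 3.3% of 191. If the last contact is the last clinic visit, g = 0 and the result is zero.

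**5. Effect on the test, by simulation.** There were 3,000 runs per scenario, with 262 patients and analysis at 37 months. Assumptions: 0 to 20% of an arm are candidates for contact-only follow-up, starting 3 months plus an exponential time (mean 6 months) after randomization; relapse is then unseen; death follows the event by a mean of 5 months. One-sided rejection rates under HR 1 (nominal 0.10, simulation error about ±0.01):

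| Candidates, control / experimental | Last contact | Last evaluation |
|---|---|---|
| 0% / 0% | 0.105 | 0.094 |
| 20% / 20% | 0.111 | 0.101 |
| 10% / 20% | 0.137 | 0.092 |
| 20% / 10% | 0.078 | 0.111 |
| 0% / 20% | 0.170 | 0.093 |
| 20% / 0% | 0.055 | 0.106 |

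Under HR 0.64, the mean estimated HR ranged from 0.607 to 0.665 with last contact and from 0.631 to 0.638 with last evaluation. Power ranged from 0.930 to 0.981 and from 0.957 to 0.971 respectively. Equal shares have almost no effect; unequal shares move the result in either direction. The simulated last-evaluation rule also drops deaths after that evaluation, so it does not test a rule that keeps them as events.

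**The case against.** The strongest reply is that the EFS wording covers only patients known to be event-free as well as alive, which the OS wording does not require. On that reading, a call that yields only vital status would not qualify as an EFS contact. The wording does narrow who is censored, but the date it assigns is still last contact, so the difference from DFS remains.

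Second, both terms are undefined, and DFS does not specify a disease evaluation, so both may in practice mean the same visit. That is fair, and it is why the fix must define the terms.

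Third, follow-up visits include an examination and CBC, and Section 12.4 keeps patients who stop therapy under its terms in endpoint follow-up. This stands and limits the problem to a small group.

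Fourth, censoring survivors back to the last evaluation while still counting later deaths treats the same interval asymmetrically. This also stands, and it is a reason to report both rules.

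A reader might go further and infer that EFS is overstated by 2 to 6 hidden relapses, or that the Phase II error rate rises to 0.17. The documents support neither. The first needs a contact without assessment in nearly every event-free patient at the lock, and no pre-lock vital-status sweep is described. The second needs arm imbalances for which the documents give no basis.

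**Conclusion.** The inconsistency is real and minor. EFS has the OS censoring date, while DFS has a different one for the same post-remission events. The plan neither defines the two dates nor includes an analysis that would show whether the choice matters. For most patients the dates should coincide. The remaining route is survival follow-up: other treatment started while in CR/CRi, if the discontinuation clause does not apply, and withdrawal before treatment.

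The size and direction of any bias cannot be determined from the documents. The calculations above show only what would follow from assumed gaps: little if the arms are alike, and a shift toward the arm with more contact-only follow-up if they are not.

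The stakes are also limited. After Amendment 04 the Phase II result no longer opens further accrual, and EFS is confirmatory only if OS is significant.

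**What to change.** In Section 13.1.1, censor EFS at the last disease evaluation showing no event, defined as a clinic visit with CBC, or a marrow examination. Use the same defined rule for DFS in Section 13.2.2. Keep last contact for OS only, and define that term too.

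State explicitly how a death after the last evaluation is handled; the EFS definition already makes death from any cause an event. Add the current last-contact rule to Section 13.2.4 as a sensitivity analysis. It follows survivors and deaths over the same interval, so it shows whether deaths after the last evaluation affect the result. While editing, say whether the discontinuation clause covers patients already in CR/CRi.

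The cost is a few sentences, slightly shorter EFS follow-up for some patients and one extra analysis. Section 5.0 already schedules the examinations and blood counts for clinical follow-up. The change should be made before the EFS analysis is run.
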